5.3.3 Carboplatin Administration Schedule

Subjects unable to tolerate cisplatin as indicated in above, may be given carboplatin instead, administered to target AUC 2. Carboplatin will be dosed using the Calvert formula:

**Total dose(mg)= (target AUC) x (glomerular filtration rate [GFR] +25)**

Calculated creatinine clearance will be used to estimate the GFR. The modified Cockcroft-Gault formula below should be used to calculate the creatinine clearance:

140 -age (yrs) x actual weight (kg) / 72 x Serum creatinine(mg/dl)

- Multiply by a factor of 0.85 if female
- Intended for ages 18-100, serum creatinine 0.6-7 mg/dl
- Carboplatin will be administered over 30 minutes.

Rev. 6/14

5.3.3.1 Dose Modifications for Carboplatin

Carboplatin Dose Modification Guidelines

Hematological toxicity	Carboplatin Dose
ANC < 1000 mm 	Hold dose
Platelet count < 75,000 mm 	Hold dose

**NOTE:** Dose modifications for carboplatin will be based on the labs on the day of treatment. If labs are above thresholds in the subsequent week, treatment can resume at the original doses.

5.3.3.1.1 Renal dysfunction: If serum creatinine increases or decreases by > 20% from

baseline, the carboplatin dose must be recalculated.

- 5.3.3.1.2 Other non-hematologic toxicities: For any grade 3 or 4 toxicities not mentioned above and excluding alopecia, nausea, dehydration and mucositis, treatment with carboplatin should be delayed until < grade 2. For grade 1 or 2 toxicities no delays will occur. If carboplatin is held > 2 weeks, it will be permanently discontinued. For grade 4 toxicity requiring hospitalization, carboplatin may be interrupted at the discretion of the treating physician.

#### 5.3.4 Radiation Dose Modifications

There will be no radiation dose modifications. Radiotherapy will be interrupted for > grade 3 radiotherapy-related toxicity except for grade 3 mucositis and skin reaction that may be managed with supportive care. Treatment may resume when toxicity resolves to grade 2.

For grade 4 toxicity requiring hospitalization (even if unrelated to radiotherapy), the treatment may be interrupted at the discretion of the treating physician.

If radiation therapy is held for toxicities (whether related to protocol treatment or not) for > 4 weeks, all protocol therapy will be discontinued.

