
For non-clinical questions (i.e., unrelated to patient eligibility, treatment, or clinical data submission) contact the CTSU Help Desk by phone or e-mail:
 
CTSU General Information Line – [name], or [contact]. All calls and correspondence will be triaged to the appropriate CTSU representative.
		

The CTSU Web site is located at https://www.ctsuo.org
		

Rev. 6/14, 2/15,  
1/16

Schema

Accrual: 515

1. Resectable oropharynx carcinoma, p16+ by IHC, PS 0-1
2. Credentialing of surgeon required as part of site participation, neck levels dissected and nodal yield (> nodes/neck)
3. Radiotherapy will be given with an intensity modulated radiotherapy (IMRT) technique. Standard ECOG credentialing through QARC will be required.
4. Stratify by current/former smoking history(≤ 10pk-yr vs. > 10pk-yr)
5. Low Risk: T1-T2, N0-N1 AND clear (≥ 3mm) margins, AND no ECE or PNI/LVI.
6. High Risk: Any of the following features: one or more positive margin(s) with any T stage, OR "Extensive" (> 1mm) ECE, OR ≥ 5 metastatic lymph nodes (regardless of primary tumor margin status).
7. Intermediate Risk: Any of the following features: one or more "close" (< 3mm) margin(s), OR "Minimal" (≤ 1mm) ECE, OR N2a (1 or more lymph node >3cm in diameter), OR N2b (2-4 lymph nodes positive, any diameter ≤ 6cm), OR with perineural invasion or lymphovascular invasion.
8. If = 2 events are observed among the first ten patients registered on Arm A within one year, currently enrolled and subsequently enrolled low risk patients who have not progressed will be treated with IMRT 50 Gy
9. Patients found to have N2c (bilateral nodes), OR N3 (>6cm node) disease on final pathologic analysis.

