#### 5.1.12 IMRT Prescription and Treatment Planning

5.1.12.1 The prescription dose will be administered with a cone-down prescription with daily doses of 2 Gy. No simultaneous in-field boost / dose-painting will be permitted. Treatment will be delivered once daily, 5 fractions per week. Treatment breaks, if necessary, should not exceed 5 treatment days and the reason(s) for the break must be clearly recorded in the treatment record. Any treatment break(s) exceeding two (2) treatment days for reasons other than toxicity/illness will be considered a protocol deviation. The reason for the missed treatment or treatments must be clearly indicated in the copy of the patients treatment record submitted to IROC Rhode Island.

- PTV-N50: will be prescribed 50 Gy in 25 daily fractions
- PTV-P60 or PTV-N60: will be prescribed 60 Gy in 30 daily fractions
- PTV-P66 or PTV-N66: will be prescribed 66 Gy in 33 daily fractions
- PTV-P70 or PTV-N70: will be prescribed 70 Gy in 35 daily fractions

As a cone-down IMRT technique will be used, a dose-summary that represents all the phases of IMRT treatment

planning shall be generated. For example, if the maximum PTV prescription for a patient is to PTV-P66, then the first phase will deliver 50 Gy to both the primary and unilateral (see section 5.1.11.2.e) or bilateral cervical nodal volumes followed by a second phase to the primary surgical bed for an additional 10 Gy and a third phase to the just the boost volume at the site of the positive surgical margin for an additional 6 Gy.

- 5.1.12.2 Tissue Heterogeneity: The dose calculation shall take into account the effect of tissue heterogeneities. The method used for tissue heterogeneity calculations shall be reported. The dose prescription is to be based on a dose distribution corrected for heterogeneities.
- 5.1.12.3 No specific beam arrangements will be specified. Commonly, a co-planar beam arrangement is used.
- 5.1.12.4 Treatment Planning Objectives: The treatment plan(s) used for each patient will be based on an analysis of the volumetric dose, including dose-volume histogram (DVH) analyses of the PTVs and critical normal structures. Inverse optimization algorithms will be used to achieve at least 95% of the volume of the specified PTVs is covered by the prescribed isodose surface while meeting the dose limitations to the delineated OARs.

Priority	Structure Name	Treatment Planning Objective				

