**Treatment Breaks:**

More than two missed treatment days for any reason other than a toxicity is considered a deviation.

Minor deviation: 3-5 days.

Major deviation: > 5 days

Evaluation After Completion of Concurrent Therapy

Patients will be re-evaluated after the completion of treatment to assess clinical and radiographic response by complete head and neck exam and imaging studies.

Patients with persistent disease will be evaluated and where indicated undergo appropriate surgical resection.

Rev. 9/16

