### 5.3 Dose Modifications

**All toxicity grades below are described using the NCI Common Terminology Criteria for Adverse Events (CTCAE) version 4.0.**

**All appropriate treatment areas should have access to a copy of the CTCAE version 4.0. A copy of the CTCAE version 4.0 can be downloaded from the CTEP website (<http://ctep.cancer.gov>).**

- 5.3.1 The use of colony stimulating factors (G-CSF, GM-CSF), and amifostine are explicitly discouraged. Erythropoietin stimulating agents, such as erythropoietin, and darbepoietin, are prohibited.

Rev. 6/14

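### Section 5.3.4 makes interruption of radiotherapy both mandatory and discretionary for radiotherapy-related grade 4 toxicity requiring hospitalization, and as printed leaves the status of other grade 3 toxicity unclear

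*Combined protocol and SAP*

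**What the plan says.** Section 5.3 sets the grading scale for what follows: "All toxicity grades below are described using the NCI Common Terminology Criteria for Adverse Events (CTCAE) version 4.0".

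Section 5.3.4 then gives three instructions that bear on this point.

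- A mandatory trigger with an exception: "Radiotherapy will be interrupted for > grade 3 radiotherapy-related toxicity except for grade 3 mucositis and skin reaction". The excepted reactions may be managed with supportive care.
- A resumption level: "Treatment may resume when toxicity resolves to grade 2".
- In a separate paragraph, a discretionary rule: "For grade 4 toxicity requiring hospitalization (even if unrelated to radiotherapy), the treatment may be interrupted at the discretion of the treating physician".

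The section ends by discontinuing all protocol therapy if radiotherapy is held for toxicity for more than 4 weeks.

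Two other places deal with breaks. Section 5.1.12.1 limits their length: "Treatment breaks, if necessary, should not exceed 5 treatment days and the reason(s) for the break must be clearly recorded in the treatment record". The treatment-breaks entry in Section 5.1.17 classifies them: "More than two missed treatment days for any reason other than a toxicity is considered a deviation". Section 5.1.18 ties chemotherapy to radiotherapy in Arm D: in a week when radiation is held, cisplatin is not given.

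**The concern.** An interruption rule should tell a site what to do for a given toxicity. Here the two paragraphs of Section 5.3.4 overlap and differ in force: the first requires interruption, the second permits it. The overlap lies among the most severe events that the section covers.

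The first paragraph also has a problem of its own. Its exception names a grade that its trigger, as printed, does not reach. A reader who relies on the sign concludes that grade 3 toxicity never requires interruption. A reader who relies on the exception concludes that it does, apart from mucositis and skin reaction.

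What is at stake is consistent handling of severe toxicity across the institutions of a multicenter trial. In Arm D the choice carries over to cisplatin through Section 5.1.18.

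**Working it through.** There is no figure to reproduce and no arithmetic applies. The check sets the sentences side by side and applies each to every combination of grade, cause and hospitalization.

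**Step 1. Reach of the trigger.** CTCAE grades are whole numbers, so a trigger above grade 3 starts at grade 4. It is limited to radiotherapy-related toxicity.

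**Step 2. Reach of the discretionary rule.** It covers grade 4 toxicity requiring hospitalization. The parenthesis in "For grade 4 toxicity requiring hospitalization (even if unrelated to radiotherapy), the treatment may be interrupted at the discretion of the treating physician" adds unrelated events without removing related ones, so both are covered.

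**Step 3. The two rules together, as printed.**

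| Toxicity | First paragraph | Second paragraph | Result |
|---|---|---|---|
| Grade 3, related, mucositis or skin reaction | Excepted, but already outside the printed trigger | Not covered | No mandatory interruption on either reading |
| Grade 3, related, other | Outside by the sign; inside by what the exception implies | Not covered | Unclear |
| Grade 4, related, not hospitalized | Mandatory | Not covered | Mandatory |
| Grade 4, related, hospitalized | Mandatory | Discretionary | Conflict |
| Grade 4, unrelated, hospitalized | Not covered | Discretionary | Discretionary |

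If the second paragraph governs the conflict row, the hospitalized case carries a weaker instruction than the non-hospitalized case in the row above it. The text does not say whether that is intended.

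**Step 4. Does the resumption level settle the trigger?** No. Resuming at grade 2 fits a trigger that starts at grade 3 and one that starts at grade 4.

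**Step 5. Does other text settle it?**

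- Section 5.1.12.1 limits the length of breaks and asks for the reason to be recorded.
- Section 5.1.17 classifies breaks as deviations.
- Section 5.1.18 says what happens to cisplatin once radiotherapy is held.
- Section 5.5 covers stopping protocol therapy, including for unacceptable toxicity.

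None of these gives a grade at which radiotherapy is interrupted, and none says which paragraph of Section 5.3.4 prevails.

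**Step 6. How far does the result depend on the printed sign?** Comparison signs are unreliable in places in the text reviewed. A note to the schema reads "If = 2 events are observed among the first ten patients registered on Arm A within one year", where Section 9 has two or more. The pack-year split in Section 1.3 likewise shows an equals sign where a not-more-than sign is expected. If the source includes grade 3 in the trigger, the exception has a function, the second row becomes mandatory, and that ambiguity disappears. The conflict row is unchanged, because grade 4 is inside the trigger on either reading.

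**The case against.** The strongest reply is that this is a drafting overlap with an evident purpose. The words about unrelated toxicity suggest that the second paragraph was meant to extend the physician's authority to events outside the first rule. Near-identical sentences close the cisplatin and carboplatin toxicity rules (Sections 5.3.2.5 and 5.3.3.1.2), which points to a repeated template clause. This explains how the overlap may have arisen, but the sentence as written still includes related events.

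On grade 3, the reply is that naming it in the exception shows it was meant to be in the trigger, and that one character in machine-read text should not carry a finding. That is fair. The damage seen elsewhere turns the sign into an equals sign, and inclusive signs survive in Section 5.3.2.1, so loss here is possible but not shown. Even as printed, this is an exception without effect that leaves other grade 3 toxicity unclear; it is not a pair of opposed instructions.

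Four stronger readings are tempting, and the documents do not support them.

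- *That all grade 4 toxicity is both mandatory and discretionary.* The table shows that only related, hospitalized events are.
- *That sites have no other guidance on breaks.* Sections 5.1.12.1, 5.1.17 and 5.5 also govern breaks and stopping. What they lack is a grade-based trigger for interruption.
- *That the ambiguity changes which breaks count as deviations.* Section 5.1.17 exempts a break for a toxicity with no grade threshold, and Section 5.1.12.1 exempts toxicity or illness. A toxicity break is exempt whichever paragraph of Section 5.3.4 is followed.
- *That it biases the 50 versus 60 Gy comparison, or affects every irradiated patient.* The same wording applies to both randomized arms, and no direction of effect can be shown. Section 9.3 judges each arm on its own confidence interval and calls the between-arm comparison exploratory. Its expected 180 intermediate-risk and 120 high-risk patients are those subject to the rule, not those for whom the readings differ.

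**Conclusion.** The point holds in two parts of unequal strength.

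First, Section 5.3.4 gives conflicting instructions for radiotherapy-related grade 4 toxicity requiring hospitalization. This follows from the current wording and does not depend on how the comparison sign is read.

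Second, as printed, the grade 3 exception has no effect, and the status of other grade 3 radiotherapy-related toxicity is unclear. This part is conditional on the sign being correct in the source document.

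The size cannot be given. The documents contain no grade 3 or 4 radiotherapy toxicity rates, so neither the number of patients in the conflict row nor any effect on treatment time can be calculated. The consequence that can be stated is practical: two sites following the text could handle the same event differently, and in Arm D the difference would extend to that week's cisplatin. The plan's endpoints, sample size, power and error rates are untouched. It is a specific defect in a safety instruction and worth correcting. No view is taken on which instruction is clinically right.

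**What to change.** Check the comparison sign in the first paragraph of Section 5.3.4 against the source document. Then reconcile the two paragraphs so that each situation has one instruction: grade 3 and grade 4, mucositis or skin reaction and other toxicity, radiotherapy-related or not, hospitalized or not. The rows of the table above can serve as the checklist. The clinical team must decide the content of each instruction.

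The treatment-break wording in Section 5.1.17 needs no change for this purpose.

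The cost is one clarifying amendment or memo to sites, with no change to the sample size or the analysis.

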### 5.4 Supportive care

#### 5.4.1 Oral Care

Dental status must be evaluated and documented by the surgeon prior to the day of surgery. A referral and consultation with a dental hygienist may be needed prior to surgery if abnormalities are noted. Dental evaluation should include: examination with radiographs, removal of diseased teeth, restorative work, periodontal therapy, smoothing of rough or irregular dental surfaces, and assessment of dental appliances for fit. In addition, patients should be assessed for trismus and if present, patients should be provided with range of motion exercise. Patients should be provided with adequate dental education including: the risk for radiation induced dental decay, methods for maintaining good oral hygiene, the appropriate use of prescription fluoride treatment, and dietary influences on oral and dental health.

Appropriate oral hygiene includes the following: brushing teeth after each meal, flossing daily, the frequent use of oral rinses with salt and/or baking soda (every two to four hours), and the daily use of prescription fluoride therapy. Additional therapy, such as the routine use of high calcium/phosphate (Caphosol) suspensions for the prevention of mucositis and dental decay should be considered.

During therapy, patients oral should be assessed on a routine basis to determine the following: compliance with oral hygiene regimens, the development of oral infections such as candidiasis, the development of oral mucositis, and the impact oral health on dietary intake. Ongoing education regarding the importance of oral care may be needed. Oral care regimens may need to be adjusted in patients who develop severe oral mucositis. Patients who develop mucosal sensitivity may require dietary counseling to help guide food choice. Patients should be told not to wear dental appliances in the presence of inflamed or ulcerated mucosa.

After therapy is completed, patients need to resume an aggressive routine dental follow-up. In addition, patients must be encouraged to continue oral hygiene regimens, the use of prescription fluoride and maintain good dietary habits.

Rev. 9/16

#### 5.4.2 Nutritional Support

At the time of diagnosis, it is strongly encouraged that all patients with head and neck cancer undergo an initial dietary assessment by a trained dietician. Nutritional status (weight loss) must be evaluated and documented by the surgeon prior to the day of surgery. A referral and consultation with a dietician may be needed prior to surgery if abnormalities are noted. Patients with weight loss and inadequate oral intake should receive a feeding tube prior to initiation of therapy. For patients with adequate oral intake, the prophylactic placement of a feeding tube is at the discretion of the treating physician. Patient should be followed by dieticians routinely throughout the course of treatment. Dietary recommendations should include: recommended total caloric intake, recommended intake of protein, daily requirement for free water, feeding tube should be placed. Close monitoring by dieticians is important for patients with feeding tubes, particularly immediately after tube placement as patients often experience problems with enteral feeding or formulations. All patients who have a feeding tube placed should be evaluated and monitored by the Dietitian and Speech Pathologist to ensure adequate nutrition and return to oral intake.

#### 5.4.3 Rehabilitation

It is strongly encouraged that all patients be referred for an assessment by a certified physical therapist after the completion of concurrent therapy. Components of the evaluation should include: neck shoulder and jaw range of motion, general conditioning level, the degree of treatment related fatigue, and postural issues. Patients with significant levels of deconditioning, postural abnormalities, or decrease in range of motion may require physical therapy. Occupational therapy may be needed in patients with extreme degrees of dysfunction. Patients with lymphedema should be referred for lymphedema therapy which should include: education, manual lymph drainage and the use of compression garments.

#### 5.4.4 Speech and Language Pathology

Swallowing assessment and therapy is considered a critical component of care for all head and neck cancer patients. An MBS study will be required at baseline and after treatment for patients from sites that have declared participation in the MBS studies, and strongly encouraged from other institutions that use the MBS study as standard-of-care for patients with swallowing dysfunction.

Assessments should be done by a trained Speech-Language Pathologists (CCC-SLP). The SLP should be consulted during treatment planning and should provide routine follow-up throughout the trajectory of the patient's treatment and recovery. The treating physician should communicate with the SLP in order to coordinate care in those patients found to have significant swallowing abnormalities. Critical component of the swallowing evaluation should include: 1) identification of any swallowing abnormalities, 2) recommendations for further testing, 3) formation of a treatment plan, 4) dietary recommendations, and 5) clear identifications of patients at risk for aspiration. Patients should be referred immediately for evaluation if any of the following "trigger symptoms" are identified: coughing or clearing the throat before, during or after eating, inability to control food, liquids or saliva in the oral cavity, complaint of difficulty swallowing or food "sticking" in the throat, nasal regurgitation of food, or pocketing of food in the cheek.

5.4.5 All supportive measures consistent with optimal patient care will be given throughout the study.

#### 5.5 Duration of Therapy

Patients will receive protocol therapy unless:

- Treatment is interrupted for 4 consecutive weeks; patient's protocol treatment will be discontinued
- Extraordinary Medical Circumstances: If at any time the constraints of this protocol are detrimental to the patient's health, protocol treatment should be discontinued
- Patient develops unacceptable toxicity; then the patient will discontinue protocol therapy
- Patients may withdraw consent and withdraw from the study at any time for any reason

#### 5.6 Duration of Follow-up

For this protocol, all patients, including those who discontinue protocol therapy early, will be followed for response until progression, even if non-protocol therapy is initiated, and for survival for 5 years from the date of registration.

## 6. Measurement of Effect

Rev. 6/14

### 6.1 Time to Progression

This interval will be measured from the date of entry on the study to the appearance of new metastatic lesions or objective tumor progression.

Rev. 6/14

### 6.2 Methods of Measurement

Imaging based evaluation is preferred to evaluation by clinical examination. The same imaging modality must be used throughout the disease evaluation.

#### 6.2.1 CT and MRI

CT and magnetic resonance imaging (MRI) are the best currently available and most reproducible methods for measuring target lesions.

#### 6.2.2 Chest X-Ray

Lesions on chest x-ray are acceptable as measurable lesions when they are clearly defined and surrounded by an aerated lung. However, CT is preferable.

